## Abstract

**Background:** Vaso-occlusive painful episodes (VOE) in sickle cell disease (SCD) are the leading cause of hospitalizations, emergency room (ED) visits, and missed school, and are associated with an increased mortality rate. There are no current therapies to relieve vaso-occlusion, with interventions limited to hydration and analgesia. Nitric oxide (NO), produced by the 5-electron oxidation of L-arginine, is a potent vasodilator and exerts pleiotropic effects on vascular and circulating blood cells, including the inhibition of platelet aggregation, down-regulation of adhesion molecules, and modulation of ischemia-reperfusion injury, all pathways adversely affected during VOE. In previous trials it has been found that pediatric SCD patients admitted with VOE have depleted plasma L-arginine levels. Additionally, a single-center randomized, double-blinded, placebo-controlled trial of arginine therapy in 54 children with VOE requiring hospitalization was completed. A reduction in total opioid use (mg/kg) by 54% and significantly lower pain scores at discharge in children who received 5 days IV L-arginine therapy every 8 hours compared to placebo, as well as a clinically relevant trend in reduced length of hospital stay of approximately 17 hours was observed. In pharmacokinetic studies, it was found that IV arginine induced a dose-dependent improvement in mitochondrial function in children with SCD hospitalized for pain.

**Design and Methods:** It is now proposed that these results are extended to a pivotal phase 3 trial of L-arginine for VOE. It is hypothesized that arginine is a safe intervention with opioid-sparing effects in pediatric patients with SCD and VOE that will decrease the time children experience severe pain. Aim 1 of this study will determine the efficacy of IV arginine therapy on the primary outcome, time-to-crisis resolution, as well as total parenteral opioid use (mg/kg) and pain scores in children with SCD and VOE compared to placebo (Efficacy). Aim 2 will monitor for safety of IV L-arginine (Safety). Aim 3 will characterize alterations in the arginine metabolome and mitochondrial function in children with SCD and VOE, and evaluate how it is impacted by IV arginine therapy (Exploratory).

**Significance:** This proposal will provide essential data for product development and FDA regulatory approval for use of arginine in SCD. Acute care of patients with SCD and pain in the ED is a neglected area of research. The results of this study may ultimately lead to change in clinical practice for children with SCD in both the ED and inpatient hospital wards. ED-based studies and novel therapies that target mechanisms of vaso-occlusion and pain are needed in SCD.

# 1 Study Summary

## 1.1 Synopsis

Table 1: Synopsis

Title:	Sickle Cell Disease Treatment with Arginine Therapy (STArT) Trial
Study Description:	The trial is designed as a double-blind, placebo controlled, randomized, phase 3, multi-center trial of IV arginine therapy in children with SCD and VOE to further knowledge on efficacy and safety of this orphan drug. The exploratory objective is to more fully characterize the arginine metabolome in children with SCD during VOE, and evaluate the effects of arginine therapy on global arginine bioavailability and mitochondrial function together with important clinical outcomes (time to VOE resolution, pain scores, total parenteral opioid use, Patient-Reported Outcomes (PROs), and hospital length of stay) in children with SCD and VOE
Objectives:	
Objective 1:
 
 
To determine the efficacy of IV L-arginine, when added to standard therapy, on the time-to-crisis resolution in children with SCD and VOE compared to placebo. Important secondary and tertiary outcomes include length of hospital stay, total parenteral opioid use (mg/kg morphine equivalents), pain scores, and patient reported outcomes (PROs) for pain in children with SCD and VOE.
 
 
Objective 2:
 
 
To determine the safety profile of IV L-arginine in the treatment of acute VOE in children with SCD. In particular, rate of acute chest syndrome, requirement for blood transfusion, oxygen use during study drug delivery, clinical deterioration and 72-hour and 28-day return visits to the ED or hospital admission will be analyzed in those receiving arginine compared to placebo.
 

	Continued on next page...

Table 1 – *continued from previous page...*

[figure not shown]
	
Objective 3:
 
 
• To further characterize alterations in the arginine metabolome and mitochondrial dysfunction in children with SCD and VOE, and evaluate how it is impacted by arginine therapy.
 
• Establish a SCD-VOE biorepository to explore future mechanistic studies.
 

Outcomes:	
Primary Outcome: time-to-crisis resolution
 
Secondary and Other Outcomes: Length of hospital stay, total parenteral opioid use, pain scores, Patient Reported Outcomes (PROs), oxygen saturation at discharge, rate of acute chest syndrome, ED or hospital readmission rates, requirement for blood transfusion, and pain medication MQS.

Study Population:	This study will enroll 360 patients in the United States that are 3–21 years old with an established diagnosis of sickle cell disease (any genotype) that are requiring medical care in an acute care setting (ED, hospital ward, day hospital, clinic) for pain not attributable to non-sickle cell causes.
Phase:	Phase 3
Description of Sites/Facilities Enrolling Participants:	
10 sites total (United States):
 
 
• Children’s Hospital Los Angeles
 
• Children’s Healthcare of Atlanta at Egleston
 
• Children’s Healthcare of Atlanta at Hughes Spalding
 
• Children’s Hospital of Philadelphia
 
• Children’s National Medical Center
 
• Medical College of Wisconsin/Wisconsin Children’s Hospital
 
• Nationwide Children’s Hospital
 
• Texas Children’s Hospital/Baylor College of Medicine
 
• UCSF Benioff Children’s Hospital
 
• Washington University/St. Louis Children’s Hospital
 

*Continued on next page...*

Table 1 – *continued from previous page...*

Description of Study Intervention:	Arginine is a safe nutritional supplement that is FDA approved in parenteral form for growth hormone stimulation testing, with nearly 50 years of safety experience through its common use by endocrinologists.  Route of administration: IV  Dose: Participants will be randomized to one of two study arms: 

• A one-time L-arginine loading dose (200 mg/kg IV) + standard dose (100 mg/kg IV TID); OR

• Placebo (normal saline) loading dose (2ml/kg IV) + 1ml/kg IV TID.

Study Duration:	6 years
Participant Duration:	28 days after discharge

## 1.2 Schema

1 - Screening CMP from a clinically ordered CMP or the last CMP in the medical record within the last 12 months will be reviewed. If there are any values within higher than protocol defined cut offs for study drug withdrawal, then a CMP is to be drawn and reviewed prior to randomization. For participants with normal past CMP, a CMP will be done on day 2.

2 - The first set of Vital Signs (including oxygen saturation) and Pain scores will be captured when the patient first presents to the Emergency Department.

This phase 3 randomized controlled trial will investigate the efficacy and safety of IV arginine for the treatment of children with Sickle Cell Disease (SCD) and acute pain. Pain is the clinical hallmark of SCD, and is the leading cause of hospitalizations, emergency room visits, missed school, and is associated with an increased death rate. Arginine is a promising new therapy that could change the way we treat acute pain in children with SCD.

### 1.3 Hypotheses

The hypotheses of this study are:

1. Arginine therapy will decrease time-to-crisis resolution in children with an acute sickle cell vaso-occlusive pain episode compared to placebo.
2. Arginine therapy will lower total parenteral opioid use (mg/kg) compared to placebo.
3. Arginine therapy will improve pain scores compared to placebo.
4. Arginine will have a similar safety profile as placebo.
5. Arginine therapy will improve global arginine bioavailability and mitochondrial activity.

### 1.4 Specific Aims

This project has the following Specific Aims:

**Specific Aim 1.** To determine the efficacy of IV L-arginine, when added to standard therapy, on the time-to-crisis resolution in children with SCD and VOE compared to placebo. Important secondary and tertiary outcomes include length of hospital stay, total parenteral opioid use (mg/kg morphine equivalents), pain scores, and patient reported outcomes (PROs) for pain in children with SCD and VOE.

**Specific Aim 2.** To determine the safety profile of IV L-arginine in the treatment of acute VOE in children with SCD. In particular, rate of acute chest syndrome, requirement for blood transfusion, oxygen use during study drug delivery, clinical deterioration and 72-hour and 28-day return visits to the ED or hospital admission will be analyzed in those receiving arginine compared to placebo.

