## 5 Data Analysis

All analyses will be undertaken by the intention-to-treat (ITT) principle. Patients who drop out (discontinue study drug) will be followed and included in the ITT analysis. All statistical tests of hypotheses will be two-sided.

The hypotheses of this study are:

1. Arginine therapy will decrease time-to-crisis resolution in children with an acute sickle cell vaso-occlusive pain episode compared to placebo.

2. Arginine therapy will lower total parenteral opioid use (mg/kg) compared to placebo.
3. Arginine therapy will improve pain scores compared to placebo.
4. Arginine will have similar safety profile than placebo.
5. Arginine therapy will improve global arginine bioavailability and mitochondrial activity.

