**Specific Aim 2: To determine the safety profile of IV L-arginine in the treatment of acute VOE in children with SCD.**

Analysis of safety outcomes (acute chest syndrome, requirement of blood transfusion, oxygen use, return visits, and clinical deterioration) will be conducted using Mantel-Haenszel chi-square tests, stratified by clinical center and age group.

Summaries of incidence rates (frequencies and percentages), intensity, and relationship to study of individual Adverse Events (AEs) by System Organ Class and Preferred Term (MedDRA) will be prepared. All AEs beginning after randomization through 14 days or until hospital discharge (whichever comes first) will be included. ED revisits and hospital admissions will be tracked through day 28 after hospital discharge. The occurrence of any adverse event will be considered as a dichotomous outcome and will be compared between groups using a Mantel-Haenszel test, stratified by clinical center and age group. Adverse events will be coded using the latest version of the Medical Dictionary for Regulatory Activities (MedDRA).

**Specific Aim 3: (Exploratory) 3a. To characterize alterations in the arginine metabolome and mitochondrial function in children with SCD and VOE, and evaluate how it is impacted by IV arginine therapy.**

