## 5.2 Sample Size Calculations and Statistical Power

Based on a previous small trial, the difference between arginine and placebo groups is approximately 0.7 days (length of stay, which parallels time to crisis resolution). A Type I error bound of 0.05 (alpha) for the primary hypothesis will be used and it will be assumed that age is not informative of outcome (a conservative bound for sample size). A simulation-based approach is used to determine the sample size required to detect a difference (shift in distribution) of 0.7 days with 85% power. In order to simulate placebo outcomes, time-to-crisis resolution data from the MAGiC trial (both arms combined, as the treatment effect did not reach statistical significance) was used. For the arginine arm, outcomes were simulated from the same distribution, shifted down by 0.7 days. 5,000 trials were simulated. This process resulted in a required sample size of 166 per arm. Accounting for withdrawal (~1%), interim efficacy monitoring (inflation of 2%), and crossover/non-adherence (3%, for example, arginine subjects who do not receive a sufficient amount of study drug) results in an overall inflation of about 8% or a total of 180 per arm. Prior to the first interim analysis (after approximately 100 subjects), the DCC and CCC principal investigators, along with the DSMB, will review, blinded to by-treatment results, summaries of the outcome distribution (mean, median, IQR with both arms combined – to compare with MAGiC data), withdrawal rate, and non-adherence rates and may adjust the target sample size accordingly, as funding allows.

Given a total sample size of 180 per arm, the effect size that will be detectable in subgroup analyses of the primary outcome, for example, a differential treatment effect based on gender or hydroxyurea use will also be reported. With 85% power, it will be possible to detect an effect size (difference in differences) of about 1.3 days, or approximately 1.9 times the main treatment effect size for which the study is powered. With 80% power, it will be possible to detect an effect size of 1.2, or 1.7 times the main treatment effect size.

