### 6.5.4 Pharmacy Monitoring

The Clinical Center pharmacy must maintain adequate study drug accountability records of all dispensed study drug. Each pharmacy will be monitored and may be requested to send copies of these documents to the Data Coordinating Center. Since this study will use a central pharmacy, that pharmacy must also maintain adequate records and will also be monitored.

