### **8.2.2 Classification of an Adverse Event (Relatedness, Severity, and Expectedness)**

**Relatedness:** The suspected relationship between study interventions and any adverse event will be determined by the site investigator using the criteria below. *Relatedness must be assessed by an investigator and may not be assessed by a research coordinator.*

**Not Related:** The event is clearly related to other factors, such as the subject's clinical state, therapeutic interventions, or concomitant drugs administered to the subject.

**Possibly Related:** The event follows compatible temporal sequence from the time of beginning the assigned study intervention, but could have been produced by other factors such as the subject's clinical state, therapeutic interventions, or concomitant drugs administered to the subject.

**Probably Related:** The event follows a reasonable temporal sequence from the time of beginning the assigned study intervention, and *cannot be reasonably explained* by other factors such as the subject's clinical state, therapeutic interventions, or concomitant drugs administered to the subject.

**Severity:** The severity, which is a measure of intensity, of clinical adverse events and laboratory abnormalities will be recorded by the site investigator and categorized. The following guidelines will be used to describe severity.

**Mild:** The event requires minimal or no treatment and does not interfere with the participants daily activities.

**Moderate:** The event results in a low level of inconvenience or concern with the therapeutic measures. Moderate events may cause some interference with functioning.

**Severe:** The event interrupts a participants usual daily activity and may require systemic drug therapy or other treatment. Severe events are usually potentially life-threatening or incapacitating. Of note, the term "severe" does not necessarily equate to "serious".

**Expectedness of the Event:** All adverse events, including serious adverse events, will be evaluated as to whether their occurrence was expected or unexpected. An AE will be considered unexpected if the nature, severity, or frequency of the event is not consistent with the risk information described for the study intervention.

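### Aim 2 frames safety by drug received, but every analysis is by ITT and no safety set is defined: a small gap that leans toward the hypothesis of similar safety

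*Combined protocol and SAP*

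**What the plan says.** The safety question appears in Section 1.1 (Objective 2) and Section 1.4 (Specific Aim 2). Both name acute chest syndrome, transfusion, oxygen use, clinical deterioration and return visits, and close with "28-day return visits to the ED or hospital admission will be analyzed in those receiving arginine compared to placebo". Hypothesis 4 in Section 1.3 reads "Arginine will have a similar safety profile as placebo", with no margin.

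The analysis population is set once, at the start of Section 5: "All analyses will be undertaken by the intention-to-treat (ITT) principle". The next sentence adds "Patients who drop out (discontinue study drug) will be followed and included in the ITT analysis". Neither sentence makes an exception for safety.

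Section 5.1, under Specific Aim 2, says the analysis of the safety outcomes "will be conducted using Mantel-Haenszel chi-square tests, stratified by clinical center and age group". It describes the adverse event tables but not who is in them. No section defines a safety or treated set, or says where a child given the wrong product is counted.

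Section 5.2 allows for "crossover/non-adherence (3%, for example, arginine subjects who do not receive a sufficient amount of study drug" when it inflates the sample size. Section 6.5.4 provides a source for what was actually given: "The Clinical Center pharmacy must maintain adequate study drug accountability records of all dispensed study drug".

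**The concern.** The aim is worded by exposure, while the analysis rule is worded by assignment. The two differ for two kinds of child.

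- **Never dosed.** A child randomized to arginine who receives none cannot have a drug reaction, yet adds to the arginine denominator.
- **Wrong product.** Site pharmacies look up each assignment by randomization number and prepare the drug (Section 4.2), so a dispensing error is possible. Under ITT, a reaction to arginine in a child assigned placebo is tabulated under placebo.

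If arginine raises the rate of an event, both cases shrink the observed difference. In an efficacy test that is conservative. Here the stated hypothesis is similarity, so the shrinkage favors it. The Abstract says the data are meant to support regulatory approval, so the safety tables will be read as a record of what happened under each product. For a rare drug-specific reaction, one event in the wrong column can change how a table reads.

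**Working it through.** **The plan's own figure.** Section 5.2 starts from 166 per arm and inflates by about 8%: 166 × 1.08 = 179.3, rounded up to 180. This reproduces the stated size. The 166 comes from a simulation on external data and cannot be re-derived from the documents. Section 5.2 is the only place that carries a non-adherence rate, and the documents give no power or margin for safety.

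**Inputs.**
- n = 180 per arm and c = 3% (Section 5.2).
- Two-sided tests (Section 5). No significance level is stated for safety, so 0.05 is assumed.
- Event rates are assumptions. Section 2.8 mentions 72-hour re-hospitalization rates of 6% and 20%, used here only to bracket the placebo rate p0. The arginine rate p1 is chosen.
- Unexposed arginine children are assumed to have the placebo event rate.

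**Dilution.** If a fraction c of the arginine arm is unexposed, the ITT rate in that arm is (1 − c)p1 + c·p0, and the ITT risk difference is (1 − c)(p1 − p0).

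With p0 = 6%, p1 = 12%, c = 3%:
- ITT arginine rate: 0.97 × 12% + 0.03 × 6% = 11.82%.
- Risk ratio: 11.82 / 6 = 1.97, against 2.0.
- Risk difference: 5.82 points, against 6.0.
- In children: 3% of 180 is 5.4, and 5.4 × 0.06 = 0.32 of an expected event, out of 180 × 0.12 = 21.6.

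**Power**, normal approximation, unstratified: Φ{[(p1 − p0) − 1.96·√(2p̄(1 − p̄)/n)] / √([p1(1 − p1) + p0(1 − p0)]/n)}, where p̄ is the mean of the two rates.
- No dilution: (0.0600 − 1.96 × 0.03017) / 0.03000 = 0.029, power 51.2%.
- c = 3%: (0.0582 − 1.96 × 0.03003) / 0.02987 = −0.022, power 49.1%.

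**Other assumed rates, same c.** The last column drops the undosed 3% from the arginine arm.

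| Placebo vs arginine | No dilution | ITT, 3% unexposed | Dosed set |
|---|---|---|---|
| 6% vs 15% | 79.8% | 77.8% | 79.3% |
| 10% vs 20% | 75.9% | 73.7% | 75.4% |
| 20% vs 35% | 89.3% | 87.6% | 88.9% |

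ITT loses about 2 power points in each row, and a dosed set recovers 1.3 to 1.7 of them.

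**Why this is a ceiling.** The only example in Section 5.2 is children who receive too little drug. They received some, so they stay in the arginine group of an any-dose set as well as under ITT, as do children who stop study drug after at least one dose. Only zero-dose and wrong-product children are handled differently, and the plan gives no rate for either.

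**The case against.** The best defense is that the plan is coherent as it stands. The Aim 2 wording may be ordinary shorthand for the two arms; Section 4.2 likewise speaks of subjects randomized to receive one or the other. Adverse events are counted from randomization (Sections 5.1 and 8.2.3) and analysed by assignment, which preserves the randomized comparison. The named outcomes can also arise from the disease itself. ITT safety tables are not wrong in themselves. Most of this stands, and it limits the point to a definition gap. It does not close the gap: no text says the aim means the assigned arm, and nothing places a child given the wrong product.

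Four stronger readings are tempting, and the documents do not support them.

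- **Relatedness is judged against the wrong product.** Section 8.2.2 says of a possibly related event: "The event follows compatible temporal sequence from the time of beginning the assigned study intervention". A reader might infer a bias from the word for assignment. It only fixes the time from which sequence is judged. Investigators are blinded, and Section 4.3.4 tells providers to assume active drug when an event is thought to be related to arginine.
- **The adverse event window fails for an undosed child.** Section 8.2.3 does run 14 days from study drug initiation, but it also closes at discharge if that comes first, and Section 5.1 counts from randomization. The window still closes.
- **Larger dilution.** A reader might assume crossover in both arms, or a rate well above 3%. Section 5.2 describes neither.
- **This is why similarity cannot be shown.** A test of difference with no margin cannot establish similarity, diluted or not. With no dilution, power for a doubling from 6% is only about 51%. That is a separate weakness, which a safety set would barely touch.

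**Conclusion.** The point holds as a minor one. The aim asks about children who received arginine, the analysis rule covers all randomized children by assignment, and no safety set or wrong-product rule connects the two. If arginine causes harm, the error leans toward Hypothesis 4.

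The size is small. For an assumed doubling from 6% to 12%, the risk ratio falls no lower than 1.97 and power drops by about 2 points, even if the plan's whole 3% were unexposed arginine children. This rests on assumed event rates, an assumed 0.05 level, the placebo event rate in unexposed children, and an unstratified approximation to the planned test. It does not show that the ITT safety tables would mislead. The practical reason to act is that the rule should be settled before unblinding, because for rare reactions the placement of one child may matter.

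**What to change.** 1. In Section 5, limit the ITT sentence to efficacy analyses.
2. In Section 5.1, Specific Aim 2, analyse adverse events and the named safety outcomes in all randomized children who received any study drug, grouped by the product actually received according to pharmacy and administration records. State in advance how a child who received both products is classified.
3. List never-dosed children and their events separately.
4. Keep the ITT safety tables as a supportive analysis, with the same stratified Mantel-Haenszel tests.

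The cost is a few sentences in the analysis plan and one further run of the same tables. The drawback is that never-dosed children leave the main safety tables and the strict randomized comparison is slightly relaxed. The retained ITT tables cover both.
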